3.5 Subgroups of Interest

Descriptive subgroup analyses may be performed by age group (6-11 years, 12-16 years, ≥ 17 years), and genetic subtype (RXLI, ARCI) on select safety endpoints.

Additionally, the following subgroups may be explored for both efficacy and safety parameters:

- Prior use of retinoids (Yes, No)
- Body Surface Area (BSA) Treated (\geq median, $<$ median)
- Age group (pediatric [≤ 17 years], adult [≥ 18 years])
- Remote Visits (no remote visits, ≥ 1 remote visit [excluding Visit 3 and Visit 8, which are per-protocol remote visits])
- Gender (male, female)
- Race (white, black or African American, Asian, other)

3.6 Methods of Pooling Data

Data from all sites will be pooled for analysis. Safety data of the optional maximal use arm may be pooled with the main study for all disposition, demographic, and safety reporting, as applicable.

3.7 Adjustments for Covariates

For all main efficacy analyses based on the Cochran-Mantel-Haenszel (CMH) approach, all stratification levels will be based on those reported in the clinical database, and not those reported through 4G Clinical's IRT system used for randomization.

3.8 Adjustments for Multiple Comparisons

Key secondary endpoints will be adjusted for multiple statistical testing through a gatekeeping hierarchical methodology, as follows: statistical significance for the first key secondary endpoint outlined above will be declared only if the primary endpoint has previously reached statistical significance. Subsequent endpoint analyses in the order presented in Section 1.4.2 will be declared significant only if the previous endpoint in order has reached statistical significance. All analyses of key secondary endpoints will be conducted at the two-sided alpha-level of 0.01.

3.9 Missing Data Handling

3.9.1 Efficacy Data

Missing data for the primary, key secondary efficacy endpoints, and select other secondary endpoints will be handled by a multiple imputation model containing baseline values, post-baseline values collected at an in-person visit (i.e. not collected remotely), treatment (TMB-001 0.05% or Vehicle for the Week 12 endpoints, TMB-001 0.05% BID or QD for the Week 24 endpoints), and randomization stratification factors. Imputation of missing data will be conducted under a working assumption of missing at random (MAR), meaning that the propensity for a data point to be missing is not related to the missing data, but it is related to some of the observed data. The following steps will be taken:

- 1) For all scores, the missingness pattern in the data will be evaluated. If the pattern is not monotone, the MCMC method of SAS PROC MI will be used to make it monotone. The minimum values for imputed variables will be set to 0, in order to force PROC MI to redraw another value for imputation when an intended imputed value is less than the 0. For IGA scores (including scaling and fissuring sub-scores) and the VIIS scores, the maximum value for imputed variables will be set to 4, in order to force PROC MI to redraw another value for imputation when an intended imputed value is greater than the 4. For the I-

NRS/WI-NRS, the maximum value for imputed variables will be set to 10. Imputed values will be rounded to the nearest integer.

- 2) SAS PROC MI will be used for imputing missing values of data with monotone missing pattern. If the MCMC method of step 1 was previously employed, one imputation will be made using each of the 50 MCMC-imputed datasets. If the MCMC method of step 1 was not previously employed, 50 imputations will be created assuming the data are missing at random (MAR).
- 3) A linear regression model will be used to impute all scores individually, using the treatment arm and non-missing scores from earlier scheduled timepoints. All response statuses will be calculated from the imputed scores.

The resulting analysis of the multiply imputed data will be outlined in Section 5.

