1.2 Schedule of Assessments (SoA)

Table 1 Schedule of Assessments

	Screening	Baseline ^b							EOS/ ET	Safety follow- up
Visit ^a	1 (could be split in 2)	2	3 (remote)	4	5	6 ^c	7	8 (remote)	9	10 ^d (remote)
	-90 to -7 Days	Day 0	Day 14 (± 1 day)	Day 28 (±4 days)	Day 56 (±7 days)	Day 84 (±7 days)	Day 112 (±7 days)	Day 140 (±7 days)	Day 168 (±7 days)	Day 182 (±2 days)
Informed consent/assent	X									
Genetic testing/confirmation	X									
Inclusion/exclusion criteria	X	X ^e								
Medical history & demographics	X	X (updated)								
Physical examination ^f	X	X ^g				X			X	
Randomization		X ^h				X ⁱ				
Demonstrate how to apply the study treatment		X								
Clinical laboratory testing ^j	X					X			X	
Concomitant medication	X	X	X	X	X	X	X	X	X	
Vital signs ^k	X	X		X	X	X	X			X
Serum hCG pregnancy test for WOCBP ^l	X									
Urine pregnancy test ^m for WOCBP ^l		X		X	X	X	X	X	X	
IGA-scaling and fissuring assessment ⁿ	X	X		X	X	X	X			X
VIIS-scaling assessment	X	X		X	X	X	X			X
Record percent of BSA in Treatment Area	X	X				X			X	

	Screening	Baseline ^b							EOS/ ET	Safety follow- up
Visit^a	1 (could be split in 2)	2	3 (remote)	4	5	6^c	7	8 (remote)	9	10^d (remote)
	-90 to -7 Days	Day 0	Day 14 (± 1 day)	Day 28 (± 4 days)	Day 56 (± 7 days)	Day 84 (± 7 days)	Day 112 (± 7 days)	Day 140 (± 7 days)	Day 168 (± 7 days)	Day 182 (± 2 days)
Itch-Numeric Rating scale ^v		X	X	X	X	X			X	
Age-appropriate Dermatology Life Quality Index ^o		X				X			X	
Ichthyosis Quality of Life- 32 ^p		X				X			X	
Photography ^q		X		X	X	X			X	
Local skin reactions ^r		X	X	X	X	X	X	X	X	
Subject eDiary: Train (T), Dispense (D), Review (R)		T+D	R	R	R	R	R	R	R	
Study treatment accountability and dispensation to subject ^s		X		X	X	X	X		X	
Adverse events		X	X ^t	X	X	X	X	X	X ^u	X

Abbreviations: BSA = Body Surface Area; CI = Congenital Ichthyosis; EOS = End of Study; ET = Early Termination; hCG = Human Chorionic Gonadotropin; IGA = Investigator's Global Assessment; VIIS = Visual Index for Ichthyosis Severity; WOCBP = Women of Childbearing Potential

- Visits at Screening, Baseline, V6 and V9 must be performed at the investigational site. Visits 4, 5, and 7 should be performed at the investigational site but can also be performed as telemedicine visits. Visits 3, 8 and 10 are scheduled remote visits.

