4	Severe	Large coalescent scales dominate, sharp edges on palpation with plate-like hyperkeratosis, numerous fissures and/or pain and symptoms that impair ADLs and/or very clinically significant fissuring severity	Large coalescent scales dominate, sharp edges on palpation with plate-like hyperkeratosis	Numerous fissures and/or pain and symptoms that impair ADLs and/or very clinically significant fissuring severity

IGA severity will be calculated as above using the scores obtained via one of the two methods below:

- On-site visual inspection
- Optional remote instead of on-site visits due to the ongoing Coronavirus Disease 2019 (COVID-19) pandemic comprised of both photographs and tele-medicine utilizing synchronous videoconferencing technology. The severity score at each visit will be based on information gathered from both sources to yield one score but remote evaluations cannot be used at Visits 1, 2, 6 or 9 unless there is a documented physical restriction to travel, such as COVID-19. All efforts will be made to have all visits on-site, the location of all assessments will be noted in the eCRF.

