8.2.4 Itch-Numeric Rating Scale (I-NRS)

Pruritus, from drug effect or allergic contact dermatitis, will be assessed with a self-administered electronic Patient-reported Outcome (ePRO) questionnaire using the I-NRS and WI-NRS daily through week 12. Subjects will indicate itch severity by selecting the severity level that best describes the worst level of itching due to CI in the past 24 hours on an 11-point scale anchored at 0 representing “no itching” and 10 representing “worst itch imaginable.” (see [Appendix 7](#)). Pruritus assessed by this evaluation should be reported as an AE only if therapy is required.

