10.3.1.4 Missing Data

Missing data for the primary and secondary efficacy endpoints will be handled by a multiple imputation model containing, at a minimum, Baseline values, post-baseline values, treatment, and randomization stratification factors. Imputation of missing data will be conducted under a working assumption of missing at random (MAR), meaning that the propensity for a data point to be missing is not related to the missing data, but it is related to some of the observed data.

The imputations will be performed for post-baseline visits. The Markov Chain Monte Carlo (MCMC) method will be used under the multivariate normality assumption to impute the missing primary and secondary efficacy endpoints by treatment group. The MCMC method will impute 50 datasets in order to estimate the treatment effect, and will be combined using Rubin’s Rule to provide an overall estimate of the difference in proportions with corresponding confidence intervals and p-value (Little 2019). For descriptive summary statistics, the median value across the imputed datasets will be used for subjects with missing endpoints.

Other methods for handling missing data may be explored for robustness. Full details will be provided in the SAP.

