3.10 Visit Windows

It is expected that all visits should occur according to the protocol schedule within the allowed protocol-specified window. All data will be tabulated per the evaluation visit as recorded on the eCRF even if the assessment is outside of the protocol-specified visit window. For the Week 12 visit (Visit 6), an analysis window will be created with a larger interval to allow in-person unscheduled visits within the interval to act as the nominal Week 12 visit; the analysis window will consist of the target day, plus or minus 14 days. For any other visit, if an unscheduled visit occurs within the allowed protocol-specified window and there are no scheduled visits reported, the unscheduled visit may act as the planned visit. If there are multiple visits in a same visit window, the median value will be used for analysis.

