5.1.2 Primary Analysis Methods

The difference in proportion of subjects achieving IGA treatment success at Week 12 (Visit 6) between the TMB-001 0.05% and vehicle groups will be the primary efficacy endpoint. For this endpoint, the IGA score will be dichotomized to "responder" (treatment success) or "non-responder" (treatment failure), where a responder is defined as at least a 2-grade improvement (decrease) in severity in the IGA score as compared to baseline. Inference will be made by comparing the proportions of

treatment successes in the TMB-001 0.05% group vs the vehicle group at Week 12 using the CMH test stratified by age (≥ 17 , 12-16 and 6-11) and genetic subtype. A two-sided alpha of 0.01 will be used for significance testing, along with 99% and 95% confidence intervals.

Missing Week 12 data will be imputed, as outlined in Section 3.9.1, and IGA responder status will be derived from the imputed values. A CMH analysis will be performed on each of the 50 imputed datasets. The results from the CMH analyses will be combined using the Wilson-Hilferty transformation by Ratitch et al. (Ratitch et al. 2013) to produce a pooled CMH statistic and p-value. The differences in proportions and standard errors will be combined using Rubin's Rule (Little 2019) the SAS PROC MIANALYZE. The pooled Mantel-Haenszel stratum-weighted estimator of the difference in proportion and the associated standard error will be used to produce the 99% confidence interval based on the large-sample approximation method for binary data without using continuity correction. The 95% confidence interval will also be provided.

A summary of the occurrences of intercurrent events of each type will be provided by treatment group.

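### SAP 3.9.1 restricts the imputation model to in-person scores: this has no workable meaning for diary itch, drops permitted remote IGA and VIIS predictors, and is not declared as a change from the protocol

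*SAP*

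**What the plan says.** Protocol 10.3.1.4 (Missing Data) calls for a "multiple imputation model containing, at a minimum, Baseline values, post-baseline values, treatment, and randomization stratification factors", with no condition on how the post-baseline values were collected. SAP 3.9.1 (Efficacy Data) narrows the post-baseline content to "post-baseline values collected at an in-person visit (i.e. not collected remotely". The same section covers the IGA, VIIS and WI-NRS scores. If the missing pattern is not monotone, an MCMC step fills the gaps. A regression step then imputes each score "using the treatment arm and non-missing scores from earlier scheduled timepoints".

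The protocol allows remote efficacy data. Under the Schedule of Assessments (1.2), "Visits 4, 5, and 7 should be performed at the investigational site but can also be performed as telemedicine visits", and Visit 3 (Day 14) is a scheduled remote visit. For the IGA, Protocol 8.2.1 says "remote evaluations cannot be used at Visits 1, 2, 6 or 9 unless there is a documented physical restriction to travel", and Protocol 8.2.2 has a matching provision for VIIS. Itch is collected with a "self-administered electronic Patient-reported Outcome (ePRO) questionnaire using the I-NRS and WI-NRS daily through week 12" (Protocol 8.2.4). SAP 5.2.2.3 maps the weekly diary averages to visits for analysis, and treats one as missing only when fewer than 4 daily scores exist.

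For the primary endpoint, SAP 5.1.2 says: "Missing Week 12 data will be imputed, as outlined in Section 3.9.1". SAP 3.10 says "All data will be tabulated per the evaluation visit as recorded on the eCRF", and requires in-person collection only of unscheduled visits that stand in for Week 12.

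**The concern.** A MAR imputation is only as good as the observed data it conditions on. If a subject's last observed score before dropping out was taken remotely and is kept out of the model, the link between that score and the dropout is lost. The MAR assumption then becomes harder to defend and the imputed value less precise.

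Three things are at stake:

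- **Itch, a key secondary endpoint.** Visit mode says nothing about the quality of a diary score, so the restriction costs information and gains nothing. The SAP addendum (2.0) reports unexpectedly few subjects with baseline WI-NRS of 7 or more, and its Section 8.0 plans for PROC MI failing to generate WI-NRS values in range. There is little information to spare.
- **IGA and VIIS.** Scores the protocol permits are lost as predictors of Week 12.
- **The primary endpoint.** The SAP does not say how an observed, permitted remote Visit 6 IGA is handled. Two programmers could treat the same subject differently.

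**Working it through.** No figure in the plan depends on this rule, so most of the check compares texts.

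**1. Is the change declared?** SAP 1.2 says the SAP sets out its differences from the protocol's analysis methods. SAP 8.0 lists two: the demotion of VIIS-50 and the move from I-NRS to WI-NRS. The in-person limit is not listed. The addendum revisits WI-NRS imputation (Section 8.0) but leaves the limit in place.

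**2. What does the limit do to WI-NRS?**
- *Literal reading.* A weekly average uses the visit date and the 6 days before it, and needs at least 4 daily scores. Only one score can fall on the visit date, so at least 4 − 1 = 3 come from other days, completed away from any visit. No post-baseline weekly average through Week 12 was collected at an in-person visit, so the model would have no observed WI-NRS to learn from.
- *By mode of the mapped visit.* The scheduled averages before Week 12 are Week 2 (Visit 3), Week 4 (Visit 4) and Week 8 (Visit 5). Visit 3 is remote by design, so 1 of 3 is always lost. All 3 are lost if Visits 4 and 5 were both by telemedicine.
- SAP 5.2.2.3 supports neither reading.

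**3. What does it do to IGA and VIIS?** A remote Visit 4 or 5 score does not enter the model. If that leaves a gap, the MCMC step fills it with a model-based draw, and the regression step then uses the draw to predict Week 12.

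**4. How much prediction is lost when Week 8 is dropped?** The documents give no correlations, so this assumes first-order autoregressive scores, unit variance, correlation *c* over 4 weeks, and Week 4 seen in person. The residual variance of Week 12 is 1 − c² given Week 8, and 1 − c⁴ given only Week 4. The ratio is 1 + c².

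| c (assumed) | With Week 8 | Week 4 only | Increase |
|---|---|---|---|
| 0.6 | 0.64 | 0.87 | 36% |
| 0.7 | 0.51 | 0.76 | 49% |
| 0.8 | 0.36 | 0.59 | 64% |

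**5. How many subjects?** SAP 1.3.3 allows for about 15% dropouts and non-evaluable subjects: 110 × 0.15 = 16.5. If 10% to 30% of these had a remote Week 8 visit (assumed), that is 16.5 × 0.10 = 1.7 to 16.5 × 0.30 = 5.0, or about 2 to 5 subjects. Subjects who stop for adverse events or lack of efficacy are non-responders anyway (SAP 5.1.1), so fewer would rely on imputation.

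**6. What if remote Visit 6 scores were set to missing?** The SAP does not say this; the sum only bounds the ambiguity. The plan states about 90% power with 110 subjects (50% against 10%, 2:1, two-sided alpha 0.01). A continuity-corrected calculation gives 89.1% at 31 + 62 evaluable, which reproduces it. The uncorrected form is Φ[(0.40 − 2.576 × SE₀)/SE₁], with SE₀ pooled and SE₁ unpooled. At 110 × 0.85 = 93.5 evaluable, SE₀ = 0.106 and SE₁ = 0.083, giving 93.8%. Removing a further assumed 10% or 20% as remote, with nothing recovered by imputation, gives 90.2% or 84.8%.

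**The case against.** The best defence is measurement validity. In Protocol Table 9, grades 1 to 4 of the combined IGA and of the scaling sub-score rely partly on palpation, which photographs and video cannot supply. Keeping remote IGA scores out of the main model is therefore defensible. That stands for the IGA. It does not carry over to WI-NRS, which has no assessor, and it is weaker for VIIS, whose descriptors in Table 10 do not mention palpation.

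The SAP also already plans completer, LOCF, tipping-point, control-based and GEE analyses (5.1.3). These are useful, but none varies whether remote scores enter the imputation. The remote-visit subgroup in 3.5 is optional.

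A reader might infer four stronger things that the documents do not support:

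- **That an observed remote Visit 6 IGA is replaced by an imputed value.** No passage sets it to missing. SAP 5.1.2 imputes missing data, and SAP 3.10 ties the in-person condition only to unscheduled Week 12 visits. The fault is silence, not a stated rule.
- **That early-termination scores are excluded.** They share the Visit 9 column, and Visit 9 must be on site, so the clause does not touch them. How they map to scheduled visits is a separate gap.
- **That the clause costs the model the Week 11 diary data.** Week 11 is unused because SAP 5.2.2.3 maps averages to visits.
- **That real scores give way to purely random values.** Imputations are drawn conditional on treatment and other scores, which is routine multiple imputation.

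**Conclusion.** The point holds as a defect in specification. The in-person limit narrows the protocol's imputation model without being declared. It cannot be applied sensibly to diary itch and conflicts with SAP 5.2.2.3. It drops permitted remote IGA and VIIS scores as predictors, and it leaves the status of a permitted remote Visit 6 score unstated.

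Its effect on the results is unknown, because the documents give no share of remote visits. The 36% to 64% rise in residual variance rests on assumed correlations, and applies only to subjects who miss Week 12 and whose Week 8 visit was remote, probably a handful. It is not a trial-level loss of precision. The power figures for remote Visit 6 scores are a worst case under a reading the SAP does not adopt; a remote Visit 6 also requires a documented travel restriction, so it should be uncommon. The itch endpoint is the most exposed, since every subject's Week 2 average is affected under either reading.

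**What to change.** 1. Exempt WI-NRS from the in-person limit, so that every visit-mapped weekly diary average with at least 4 daily scores enters the imputation model whatever the visit mode.
2. State that a remote Visit 6 IGA or VIIS score taken under a documented travel restriction is analysed as observed, or say openly that it is set to missing. Apply the same rule in the completer analysis.
3. The in-person-only model may stay primary for the IGA, given palpation. Add a sensitivity analysis that admits permitted remote Visit 4, 5 and 6 IGA and VIIS scores.
4. List the narrowing of Protocol 10.3.1.4 in SAP 8.0, with the reason.

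The cost is a few lines of SAP text, a little extra programming and one more sensitivity analysis. No new data are needed: Protocol 8.2.1 and 8.2.2 already have the location of each assessment noted in the eCRF.

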5.2.2 Analysis Methods

Statistical testing will be performed on the key secondary efficacy endpoints using a two-side alpha of 0.01, according to the following hierarchical order.

5.2.2.1 IGA Clear Score Responders at Week 12

The difference in proportions of subjects with IGA score of clear or almost clear (henceforth referred to as 'IGA clear score responders') versus mild/moderate/severe will be computed at Week 12, between the TMB-001 0.05% and vehicle treatment groups.

The difference in proportions will be calculated in a similar manner as the primary efficacy endpoint using the CMH test, including the use of 50 multiply imputed datasets combined using the Wilson-Hilferty transformation for the pooled CMH statistic and Mantel-Haenszel stratum-weighted difference in proportions combined using Rubin's rule. Results will be provided using the primary efficacy data presentation.

5.2.2.2 IGA-Scaling Sub-Score Responders at Week 12

The difference in proportions of subjects with a ≥ 2 point change from baseline in IGA-scaling severity sub-scores (henceforth referred to as 'IGA-scaling sub-score responders') will be computed at Week 12 among subjects who have a score of ≥ 3 at baseline, between the TMB-001 0.05% and vehicle treatment groups.

The difference in proportions will be calculated in a similar manner as the primary efficacy endpoint using the CMH test, including the use of 50 multiply imputed datasets combined using the Wilson-Hilferty transformation for the pooled CMH statistic and Mantel-Haenszel stratum-weighted difference in proportions combined using Rubin's rule. Results will be provided using the primary efficacy data presentation.

5.2.2.3 Worst Itch-QoL (WI-NRS) Responders at Week 12

The difference in proportions of subjects achieving a ≥ 4 -point improvement from baseline in weekly Worst Itch-QoL scores on the WI-NRS (henceforth referred to as 'Worst Itch-QoL (WI-NRS) responders') will be computed at Week 12, between the TMB-001 0.05% and vehicle treatment groups. Only subjects with baseline WI-NRS scores of ≥ 7 will be included in this analysis.

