The WI-NRS scores will be collected daily, where the weekly average scores will be mapped to each protocol-specified visit and used for analysis, as appropriate. The daily scores to be used will depend on actual visit dates; daily scores of the 6 days prior to the Week 12 visit will be averaged with the daily score reported on the Week 12 visit date to create the weekly average for the Week 12 visit. A weekly average can only be computed if there are ≥ 4 daily scores reported, otherwise the weekly score will be considered missing. Early subjects do not have daily scores collected prior to baseline (in order to derive baseline weekly averages). In such cases, the single baseline score will be used for analysis.

The difference in proportions will be calculated in a similar manner as the primary efficacy endpoint using the CMH test, including the use of 50 multiply imputed datasets combined using the Wilson-Hilferty transformation for the pooled CMH statistic and Mantel-Haenszel stratum-weighted difference in proportions combined using Rubin's rule. Results will be provided using the primary efficacy data presentation.

For completeness, a descriptive analysis of the I-NRS will also be provided, as applicable.

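### Imputed WI-NRS values are rounded to integers but observed Week 12 values are weekly averages, so the 4-point response cut shifts by +0.5 to about -0.36 point for imputed subjects, depending on the baseline fraction

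*SAP*

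**What the plan says.** SAP 3.9.1 imputes in three steps. Step 1 uses MCMC to make the missingness pattern monotone and sets limits (0 to 4 for IGA and VIIS, 0 to 10 for I-NRS/WI-NRS). It then adds: "Imputed values will be rounded to the nearest integer". Step 2 creates the 50 monotone imputations. Step 3 specifies the model, "A linear regression model will be used to impute all scores individually", and adds "All response statuses will be calculated from the imputed scores". Steps 2 and 3 do not repeat the limits or the rounding.

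For the observed score, SAP 5.2.2.3 says that "the weekly average scores will be mapped to each protocol-specified visit and used for analysis", with no rounding. Missing weeks are defined by "A weekly average can only be computed if there are ≥ 4 daily scores reported, otherwise the weekly score will be considered missing". The responder needs a fall of at least 4 points, described as "improvement from baseline in weekly Worst Itch-QoL scores on the WI-NRS", and "Only subjects with baseline WI-NRS scores of ≥ 7 will be included in this analysis". Early subjects have no daily scores before baseline: "In such cases, the single baseline score will be used for analysis". That single score is an integer, because the scale in Protocol Appendix 7 offers only whole numbers from 0 to 10.

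This is the third of three key secondary endpoints, tested hierarchically at two-sided 0.01 (SAP 1.4.2 and 3.8). Addendum section 8.0 returns to WI-NRS imputation but changes only how out-of-range values are handled. Otherwise SAP 3.0 still applies, so the rounding stands.

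**The concern.** Rounding to an integer is right for a score observed as an integer, such as the IGA or a single VIIS area. A seven-day mean is not such a score. Take a baseline of 7. An observed weekly mean of 3.29 is an improvement of 3.71 and fails. The same value, if imputed, becomes 3, an improvement of 4, and passes. Response is thus defined differently according to whether the subject's diary was complete.

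At stake is a multiplicity-controlled endpoint in a subset that addendum section 2.0 describes as unexpectedly small, where a few reclassified subjects could be visible. The additional analysis there (baseline of at least 4) uses the same method and inherits the same mismatch.

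**Working it through.** The plan gives no figure for this endpoint to reproduce. The inputs taken from it are the rounding rule, the weekly-average definition, the 4-point threshold, the baseline minimum of 7, the 0 to 10 range, and the roughly 15% dropout and non-evaluable rate in SAP 1.3.3. The Week 12 distribution, the baseline mix and the 25% missingness are assumptions.

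**Shift of the cut.** Write baseline as b + f, with b an integer and 0 ≤ f < 1.
- Unrounded score x: response if x ≤ b + f − 4.
- Rounded score: response if x < b − 4 + 0.5.
- Shift = (b − 4 + 0.5) − (b + f − 4) = 0.5 − f.

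For seven-day baseline averages:

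| f | 0 | 1/7 | 2/7 | 3/7 | 4/7 | 5/7 | 6/7 |
|---|---|---|---|---|---|---|---|
| Shift | +0.50 | +0.36 | +0.21 | +0.07 | −0.07 | −0.21 | −0.36 |

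Four fractions loosen the cut and three tighten it; the mean is +0.07. With four, five or six daily scores the largest fractions are 3/4, 4/5 and 5/6, giving shifts of −0.25, −0.30 and −0.33, so the range above covers them. An example of tightening: at baseline 7.86 an observed 3.71 (improvement 4.14, from unrounded sevenths) passes, while an imputed 3.71 becomes 4 (improvement 3.86) and fails.

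**Effect on an imputed subject.** Let F be the distribution function of a normal truncated to 0–10, SD 2.2. For baseline B, the unrounded response probability is F(B − 4) and the rounded one is F(⌊B − 4⌋ + 0.5). These are averaged over equally weighted baselines: 7, 8, 9, 10 (integer), or every seventh from 7 to 10. Rises are taken before rounding the percentages.

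| Week 12 mean | Integer: unrounded → rounded | Rise | Sevenths: unrounded → rounded | Rise |
|---|---|---|---|---|
| 3 | 70.2% → 77.0% | +6.88 | 71.1% → 72.4% | +1.35 |
| 4 | 56.6% → 64.6% | +7.95 | 57.0% → 58.5% | +1.48 |
| 5 | 41.9% → 50.0% | +8.15 | 41.5% → 43.0% | +1.44 |
| 6 | 28.1% → 35.4% | +7.35 | 27.2% → 28.4% | +1.24 |

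**Effect on one arm.** At 15% imputed, integer baselines add 0.15 × 6.88 = 1.0 to 0.15 × 8.15 = 1.2 points. Sevenths add about 0.2.

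**Effect on the treatment difference** (active mean below vehicle mean, six pairs, integer baselines):
- Equal 15% missing: lowest at means 3 and 5, 0.15 × (6.88 − 8.15) = −0.19; highest at means 5 and 6, 0.15 × (8.15 − 7.35) = +0.12.
- 25% missing on active, 15% on vehicle: from 0.25 × 6.88 − 0.15 × 8.15 = +0.50 to 0.25 × 8.15 − 0.15 × 7.35 = +0.93.
- 15% on active, 25% on vehicle: from 0.15 × 8.15 − 0.25 × 7.35 = −0.62 to 0.15 × 6.88 − 0.25 × 8.15 = −1.01.

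With baselines in sevenths, the same sums stay within 0.04 points at equal missingness and within 0.2 points at 25% versus 15%.

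**The case against.** Four points can fairly be made for the plan.

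First, the rounding sentence sits in step 1, which only makes the pattern monotone. A missing Week 12 score at the end of the sequence is filled by the step 3 regression, where rounding is not mentioned. This stands as an ambiguity. The 0 to 10 limits also appear only in step 1, so a global reading is natural, but it is implied. Two programmers could produce different responder counts, which is itself a reason to amend.

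Second, few subjects are exposed. Discontinuation for adverse event or lack of efficacy, and use of prohibited medication, count as non-response under the estimand (SAP 5.2.1), so rounding cannot change those outcomes. This stands and makes the affected share smaller than total missingness.

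Third, SAP 5.2.3 already plans a completer analysis in the ITT and PP populations. That analysis would expose the effect but does not correct the main analysis.

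Fourth, the rule is identical in both arms and largely cancels. This stands. A reader might infer from the 0.01 test that the error rate is inflated. The documents do not support that: a material bias needs unequal missingness or an unequal baseline mix between arms, and neither is shown. A reader might also infer that imputed subjects always face an easier threshold. That is wrong for baseline fractions above one half.

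**Conclusion.** The mismatch of scales is real under the natural reading of SAP 3.9.1, and the addendum does not remove it. Its direction depends on baseline: looser for integers and fractions below one half, neutral at one half, stricter above. Only for integer baselines is the loosening systematic, and the documents do not say how many early subjects have a single baseline score.

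The effect on an imputed subject's response is appreciable with integer baselines and slight with weekly-average ones. The effect on the treatment difference is small and can take either sign. These sizes rest on the assumed truncated normal distributions, equally weighted baselines, and missingness of 15% (the plan's overall figure, not specific to this endpoint) or 25% (assumed). The 0.5 − f shift needs none of these assumptions. The point is worth correcting because the endpoint is multiplicity-controlled and the repair is nearly free, not because the test is shown to be invalid.

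**What to change.** In SAP 3.9.1, or by a further addendum:
- Limit integer rounding to scores observed as integers: IGA and its sub-scores, individual VIIS areas, and the Week 24 I-NRS/WI-NRS, which is a single-day score (SAP 5.4.3). Exempting the WI-NRS at all visits would create the reverse mismatch at Week 24.
- Leave imputed weekly-average I-NRS/WI-NRS values through Week 12 unrounded, kept within 0 to 10 by redraw or by the truncation in addendum section 8.0.
- State that the same range and rounding rules apply to the regression imputations of steps 2 and 3.

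The cost is two or three sentences and a small change to the imputation program. No data collection, sample size or testing order changes. Imputed and observed subjects then face the same 4-point cut.
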